6.2.8 Multiple measurements

Here, a multiple measurement refers to a combination of analysis visit and timepoint where there are more than one value recorded for a given parameter.

Unless otherwise specified, if there are multiple measurements for a given parameter-visit-timepoint combination, values from the measurement that was performed last will be used.

For 12-lead ECG parameters (specifically, all parameters in the ADEG dataset), the mean value of all multiple measurements will be used for parameters measured quantitatively. For parameters measured qualitatively, the most severe value will be used.

6.2.9 Multiple timepoints

The primary efficacy model will include all planned post-baseline visits up to the Week 12 visit. Additional analyses of primary efficacy will include all planned study visits. Included timepoints for other endpoints will be described separately. Baseline measurements of outcome variables will be included as covariates in the models. The MMRM will be used to estimate the covariance between measurements for a given subject, without assuming any specific structure a priori. Planned visit will be included as a factor in the model. For slope analyses, the actual study day of the visit will be used. All time-to-event analyses will be performed up to the first event only.

6.2.10 Checking model assumptions

Assumptions for parametric testing will be checked by visual inspection of residuals. If the residuals do not sufficiently closely follow the distribution assumed by the model in question, non-parametric comparison methods or use of transformation will be considered.

6.2.11 Transformations

No data transformations are planned.

6.2.12 Multicentre studies

The study activated a total of 104 centres for recruitment in 14 countries.

Subject disposition will be tabulated by centre and by country of randomization. A summary table showing the number of patients screened, randomized, discontinued, and completed for each centre will be provided.

For statistical models, centre will be included as a random effect, where applicable. A treatment by centre interaction will be investigated in the primary efficacy analysis, if feasible. Pooling small centres will be considered if there is reason to suspect impactful centre differences. However, the primary analysis will drop the centre random effect, if it leads to convergence issues.

6.2.13 Interim analyses and data monitoring

Two interim analyses will be conducted: first when approximately 50% of the subjects, and second when all of the subjects have completed their Week 12 study visit (Visit 5).

An independent DSMB will perform and evaluate the interim/futility analyses and make recommendations for the study conduct. The DSMB will have access to the treatment code through an independent reporting statistician, and the DSMB will have a possibility review any unblinded information in a separate closed session. Details on the composition and responsibility of the DSMB are outlined in a DSMB charter. Based on the futility analyses the DSMB will give its recommendation “continue” or “not continue” the study to the Orion Executive Committee (OEC).

Futility will be evaluated in the primary efficacy endpoint, and the time to respiratory event endpoint. We estimate that approximately 40% and 85% of the respiratory events will have accumulated at the time of the planned interim analyses.

In addition the SVC and respiratory event endpoints, accumulated data for the ALSFRS-R, CGI and Borg CR 10 will be summarized at the interim analyses.

Non-binding stopping criteria will be based on O’Brien-Fleming type boundaries (Lan GKK et al., 1983, O’Brien PC et al., 1979) and are detailed in the DSMB SAP.

As the interim analyses only allow early stopping for futility, not for efficacy or sample size re-estimation, adjustments to significance levels are not made in the final analyses.

6.2.14 Subgroups

Subgroups will be analysed for evidence of a differential treatment effect. A treatment-by-subgroup interaction term will be added to the statistical model, and the stratification factor, if present, will be removed. Subgroups defined by the following variables will be investigated:

1. Age (< 65, 65–74, ≥ 75)
2. Sex (male, female)
3. Race (white, non-white)
4. Country
5. Region (North America, rest of the world)
6. Site of onset (bulbar, spinal)
7. Edaravone use (yes, no)
8. Riluzole use (yes, no)
9. Combination of edaravone and riluzole use (4 groups)
10. Below median disease duration (time from symptom onset to randomization)
11. Above median time from symptom onset to diagnosis
12. Acetylation status (slow, fast; see 7.7)
13. Renal impairment status (see 7.9.3)
14. Hepatic impairment status (see 7.9.3)
15. Below median SVC (sitting) at screening
16. Below median SVC (supine) at baseline
17. King's clinical stage at baseline (see 7.5.2.1)
18. Below median ALSFRS-R at baseline
19. ALS progression rate at baseline (< 1 point/month, ≥ 1 point/month)
20. ALS progression rate at baseline (observed tertiles)
21. Dose change category (see section 7.4)

Subgroup analyses will be performed for the primary efficacy endpoint, the time to respiratory event endpoint, and the slope of change in the ALSFRS-R total score endpoint. Ad-hoc analyses of other endpoints may also be performed, and included in the study report.

Summary of AEs and AESIs will be presented in the subgroups of: age; sex; race; BMI; edaravone use; riluzole use; acetylation status; baseline medical history groups of interest (see 7.3); baseline renal and hepatic impairment status; and baseline King's clinical stage.

Adverse events will be summarised by patients having heart rate increase related dose changes. Drug-drug-interactions with medication groups of interest (see 7.10.1) will be evaluated for blood pressure, pulse rate, and QT interval. Dose changes will be further presented by acetylation status.

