5. DETERMINATION OF SAMPLE SIZE

Sample size estimation is based primarily on supine SVC results from the study 3119001 LEVALS (Table 1). LEVALS had placebo-controlled data only up to 2 weeks, and therefore extrapolation of the results was needed. The placebo effect from phase II tirasemtiv trial BENEFIT-ALS (Shefner JM et al., 2016) was also evaluated.

Assuming a difference of at least 3.6% in change from baseline supine SVC between treatment groups and a common standard deviation of 10%, 164 evaluable subjects per group in a 1:1 allocation ratio have 90% power to detect a statistically significant difference in a two-sided, 5% α -level, two group T-test. Using a 2:1 allocation ratio, randomisation of 450 subjects to the study (approximately 300 levosimendan and 150 placebo treated subjects) allows for a total dropout rate of approximately 20%.

Table 1. Mean (SD) change from baseline SVC (supine) %-predicted in LEVALS

Treatment	2 weeks	12 weeks
Levosimendan 1 mg x 2	+2.4 (8.3)	-4.9
Levosimendan 1 mg x 1	+0.8 (8.6)	
Placebo	-3.6 (9.4)	-17.7 ¹
Placebo (BENEFIT-ALS)	-1.4	-8.5

¹ Extrapolated from the data

SD = standard deviation

Based on the dexpramipexole phase III study EMPOWER (Cudkowicz ME et al., 2013), a 12 point reduction in total ALSFRS-R score and a 15% mortality rate at 12 months can be assumed

in placebo treated patients. Assuming a 10 point decline in ALSFRS-R, with a standard deviation of 8 points, and a 20% relative improvement in survival, 450 patients provide approximately 80% simulated power to detect a statistically significant difference using a joint rank test. With 450 subjects and assuming a 48-week levosimendan event rate of 73% and hazard ratio of 0.70, time to respiratory event has approximately 70% power to detect a statistically significant difference using a log-rank test.

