6.2 Statistical issues

6.2.1 Randomization

Randomization will be conducted centrally using Medidata Rave RTSM. The subjects will be allocated to 2 parallel groups receiving either levosimendan 1-2 mg daily or placebo in 2:1 ratio.

The estimated number of sites is approximately 100 and randomization will not be stratified by centre. Randomization will be stratified by the following factors:

1. Bulbar onset
2. Edaravone use
3. North American region

The stratification variable used to adjust the statistical models will combine all three randomization factors into a single factor with $2^3 = 8$ distinct levels.

Due to data entry errors at randomization, levels of the stratification factors used for randomization may differ from final CRF data. Primary analyses will be conducted with the levels of stratification factors used for randomization (STRATAR in ADSL), while final CRF data will be used in a sensitivity analysis (STRATAV in ADSL; see 7.5.4).

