6.2.2 Significance level and confidence intervals

Two-sided tests with a significance level of 5% will be used throughout the analyses. Corresponding 95% confidence intervals will be calculated for model-based contrasts, comparing the active treatment to placebo, using model-based standard error estimates.

The study has interim analyses that allow early stopping for futility, but not for efficacy. Therefore, we do not make adjustments to the significance levels in the final analyses.

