Primary efficacy will be evaluated based on the fitted model, using contrasts to obtain an estimate of the difference between the treatment and placebo at the Week 12 visit (Visit 5). Statistical significance of the Week 12 treatment difference will be tested. All SVC measurements from planned study visits prior to the Week 12 visit will be included in the estimation of the model.

SAS code in the following fashion will be used to perform the computations:

```
proc mixed data = ADEFF order = data alpha = 0.05 covtest;
  where ITTFL = "Y" and PARAMCD = "SVCPPSUP" and
    AVISIT in ("Week 2", "Week 4", "Week 8", "Week 12");
  class TRTP(ref = "PLACEBO") AVISIT STRATAR USUBJID SITEID;

  model CHG = BASE STRATAR TRTP AVISIT TRTP * AVISIT / ddfm = KR;
  repeated AVISIT / subject = USUBJID type = UN R;
  random SITEID / type = VC;

  estimate "Treatment Difference at Week 12"
    TRTP 1 -1 TRTP * AVISIT 0 0 0 1 0 0 0 -1 / cl;
run;
```

In the primary analysis, missing data are imputed using multiple imputation. As a result, the analysis above is repeated for each of the imputed data sets with the use of a by-statement. The analysis results are then pooled for inference according to the methods described in 6.2.5.

In additional analyses, data from all planned visits through 48 weeks will be included in the MMRM, and the treatment effect will be estimated with contrasts at each study visit. Further, a random slope model will be fitted, with visits' actual study days replacing the visit factor.

Changes in SVC (supine) between the last measurement while on treatment and the post-treatment measurement from their End of Study visit will be described.

Subgroup analyses will be conducted by removing the randomization stratum effect from the primary analysis model, and including the subgroup term and its interaction with treatment.

Descriptive statistics of SVC (supine) will also be presented by visit, treatment group, and angle of measurement position. The angle is categorised into three groups: 1) completely flat (0 degrees); 2) slightly elevated (up to 15 degrees); 3) unable to perform supine (> 15 degrees). The effect of angle of measurement will also be explored in an additional analysis, where the angle will be included as a factor in the primary analysis MMRM.

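### The subgroup models drop the randomisation strata even for the 16 of 21 subgroup variables that do not overlap with them: a small, avoidable loss in supportive analyses

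*SAP*

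**What the plan says.** SAP 6.2.14 lists 21 subgroup variables, to be examined for three endpoints: supine SVC, time to respiratory event, and the slope of the ALSFRS-R total score. The general model rule is "A treatment-by-subgroup interaction term will be added to the statistical model, and the stratification factor, if present, will be removed". SAP 7.5.1.1 repeats it for SVC: "Subgroup analyses will be conducted by removing the randomization stratum effect from the primary analysis model", with the subgroup term and its interaction with treatment put in.

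SAP 6.2.1 defines what is removed: "The stratification variable used to adjust the statistical models will combine all three randomization factors into a single factor". The three factors are bulbar onset, edaravone use and North American region, giving 8 levels. The as-randomised version is STRATAR and the CRF version is STRATAV.

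STRATAR is a fixed effect in the primary MMRM (SAP 7.5.1.1) and a covariate in the Cox model (SAP 7.5.2.3). The ALSFRS-R total slope model is not written out in SAP 7.5.2.1, so whether it contains the factor is not stated. Neither subgroup passage gives a reason for the removal. SAP 7.5.2 classes analyses outside the testing hierarchy as supportive.

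**The concern.** Removing the combined factor makes sense where the subgroup variable is one of its components or is nested with one, because the two terms then overlap. The rule, however, has no exception for the variables where this does not arise. Age, sex, acetylation status, baseline SVC, baseline ALSFRS-R and the rest can sit beside STRATAR without difficulty. The SAP does this itself in 7.5.4.9, which adds riluzole use to the primary SVC model and leaves the strata in. The riluzole subgroup analysis of the same endpoint takes them out.

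Two things are at stake. Interaction tests have little power, and leaving out a prognostic baseline factor widens their standard errors. In addition, the hazard ratio is non-collapsible: its value depends on which prognostic covariates are in the model. Subgroup hazard ratios without strata would be read against an overall hazard ratio that is adjusted for them.

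**Working it through.** **Overlap count.** Of the 21 variables in SAP 6.2.14, those sharing information with the stratum by definition are country (nested in region), region, site of onset, edaravone use, and the edaravone/riluzole combination. That is 5, leaving 21 − 5 = 16. Within the 5 the rule still takes too much: for site of onset, edaravone use and region go as well.

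**The plan's own figure first.** SAP section 5 states "Assuming a difference of at least 3.6% in change from baseline supine SVC between treatment groups and a common standard deviation of 10"%, and "164 evaluable subjects per group in a 1:1 allocation ratio have 90% power to detect a statistically significant difference". With two-sided 5% testing, n per group = 2 × (1.960 + 1.282)² × (10/3.6)² = 162.2, so 163 by the normal approximation; power at 164 is 90.2% (noncentral t). The stated 164 is reproduced. Randomising 450 at 2:1 with about 20% dropout leaves about 360 evaluable (240 and 120).

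**SVC: precision.** The documents do not say how much residual variance the strata explain. Call that share R², assumed to lie between 1% and 10%, and take SD 10 as the residual SD with strata kept. Without strata the SD is 10/√(1 − R²). For a subgroup holding half the evaluable subjects (120 and 60), SE = SD × √(1/120 + 1/60), the interaction SE between two equal halves is √2 times that, and power for 3.6 points is Φ(3.6/SE − 1.96).

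| Model | SD | SE, half subgroup | Power for 3.6 | Interaction SE | SE increase |
|---|---|---|---|---|---|
| Strata kept | 10.00 | 1.58 | 62.4% | 2.24 | – |
| Removed, R² 1% | 10.05 | 1.59 | 62.0% | 2.25 | 0.5% |
| Removed, R² 2% | 10.10 | 1.60 | 61.6% | 2.26 | 1.0% |
| Removed, R² 5% | 10.26 | 1.62 | 60.2% | 2.29 | 2.6% |
| Removed, R² 10% | 10.54 | 1.67 | 57.9% | 2.36 | 5.4% |

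Expressed as sample size, the loss is R² × 360, or about 4 to 36 subjects.

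**SVC: bias.** A linear simulation (600 runs, 360 subjects, stratified 2:1 permuted blocks, true effect 3.6) gave mean subgroup estimates with and without strata of 3.68 and 3.67 (R² 2%), 3.63 and 3.63 (5%), and 3.48 and 3.48 (10%). The gaps from 3.6 are simulation error common to both models. Within one simulated trial the two estimates differed by 0.18 to 0.33 points on average, against an SE of about 1.6. At R² 10% the model-based SE without strata averaged 1.67 while the estimates actually varied with SD 1.57, so the reported interval is too wide rather than too narrow.

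**Time to respiratory event.** Cox models were fitted to 300,000 simulated subjects with true hazard ratio 0.70, 2:1 allocation, and event rates scaled to the planned 73% on levosimendan. All prognostic inputs are assumptions: prevalences of 20% (bulbar onset), 20% (edaravone) and 40% (North America), the onset hazard ratio shown, and its square root for each of the other two factors.

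| Onset hazard ratio | Adjusted for strata | Unadjusted | Log hazard ratio weaker by |
|---|---|---|---|
| 1.25 | 0.702 | 0.704 | 1% |
| 1.5 | 0.696 | 0.702 | 2% |
| 2.0 | 0.700 | 0.716 | 6% |
| 3.0 | 0.698 | 0.732 | 13% |

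A second set of assumptions (onset hazard ratio 1.8 at 25% prevalence, region 1.3 at 35%; 120 trials of 450) gave 0.706 adjusted and 0.718 unadjusted: ln 0.718 / ln 0.706 = 0.331/0.348 = 0.95, or 5% weaker.

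**The case against.** The strongest defence is that a uniform rule is simple, avoids overlap everywhere, and gives all 21 analyses one common adjustment set. Any subgroup model already differs from the primary model by its main-effect and interaction terms. The SVC model also keeps baseline SVC and, unless it is dropped for non-convergence, the random centre effect. Centres lie within regions, so part of what the strata explain is retained and the true loss is probably towards the lower end of the table.

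For the Cox endpoint the shift is small beside sampling error. Simulating the second set of assumptions in a half-sample subgroup (400 trials of 450) gave 0.697 adjusted and 0.705 unadjusted, with SE 0.160 for both. The log shift is 0.361 − 0.350 = 0.011, about 7% of one SE. The interaction SE was 0.227 and 0.226, so the SVC precision argument does not carry over to the Cox model.

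All of this stands as to size. It does not supply a reason for removing the factor where nothing overlaps. Each analysis is one interaction model over all subjects, so keeping STRATAR costs 8 − 1 = 7 main-effect parameters, as in the primary model, however small a subgroup is.

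A reader might also infer more than the documents support:

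- That SVC subgroup estimates are biased or conflict with the primary estimate. In a randomised linear model they are not biased, and the simulation agrees.
- That bulbar onset was chosen as a stratification factor because it is prognostic. Protocol 5.4 gives only balance of allocation as the reason.
- That a published forest plot would mix two models. Neither document plans a forest plot; the comparison arises only if subgroup and overall results are shown together.
- That the slope analysis is affected. Its model is not written out, and the rule applies only where the factor is present.

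**Conclusion.** The rule is broader than overlap requires, it is unexplained, and it differs from the SAP's own handling of riluzole in 7.5.4.9. The consequences are modest.

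- **SVC:** no bias. Reported SEs are about 0.5% to 5% larger for an assumed R² of 1% to 10%, less if baseline SVC and centre already carry part of it, and about unchanged if the strata are not prognostic.
- **Time to respiratory event:** subgroup hazard ratios are less conditional than the stratum-adjusted overall one and slightly closer to 1. With moderate assumed prognostic effects, 0.70 becomes about 0.70 to 0.72; it reaches 0.73 only with an onset hazard ratio of 3. This is a change in what is estimated, not an error in estimation.
- **ALSFRS-R total slope:** cannot be judged from the documents.

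No confirmatory conclusion changes, because subgroup analyses lie outside the testing hierarchy. This is a low-cost improvement to supportive analyses, and its exact size cannot be fixed from the documents.

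**What to change.** In SAP 6.2.14 and 7.5.1.1, replace the blanket removal with two rules:

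- For the 16 non-overlapping variables, keep STRATAR and add the subgroup term and its interaction with treatment.
- For the 5 overlapping variables, replace STRATAR with the remaining stratification factors as separate main effects, using as-randomised values:
  - site of onset: region and edaravone use;
  - region and country: onset and edaravone use;
  - edaravone use and the edaravone/riluzole combination: onset and region.

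State as well whether the ALSFRS-R total slope model contains the strata, so that it is clear whether the rule applies there.

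The cost is small but not nil. STRATAR is a single combined variable, so its components must be available separately, and the 5 overlapping analyses need their own model lines. Those models will still not match the primary model exactly, because the 8-level factor is replaced by additive terms. No new data are needed, and the primary and hierarchical analyses are untouched.

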5.3.2 Dose adjustment

The daily doses of oral levosimendan will be 1-2 mg depending on the tolerability (mainly judged by HR). The subjects will start with a 1 mg dose (in the morning) for 2 weeks.

HR will be assessed in the morning before study drug intake:

- At visit 2 (2 weeks):
 - If the HR in the 12-lead ECG has increased ≤ 15 bpm from baseline, the subject will increase the dose to 1 mg b.i.d.
 - If the HR in the 12-lead ECG has increased > 15 bpm from mean baseline value, the subject will continue with the 1 mg once daily. If the increase in HR is > 30 bpm in 3 separate recordings, the subject must discontinue the study treatment (see section 4.5).

- At visit 3 (4 weeks) or later visits:
 - If the HR in the 12-lead ECG has increased ≤ 20 bpm from baseline, no changes to the dosing regimen are made.
 - If the HR in the 12-lead ECG has increased > 20 bpm from baseline in 3 separate recordings taken within 5-10 minutes from each other, the subject will decrease the dose back to 1 mg once daily if treated with 1 mg b.i.d. In case the increase in HR is > 30 bpm in each of the 3 separate ECG recordings, the HR must be checked again at an additional visit approximately 2 weeks after the dose decrease. If the increase > 30 bpm is recorded at the dose level of 1 mg once daily in 3 separate recordings, the subject must discontinue the study treatment (see section 4.5).

Administration of placebo (1 or 2 capsules per day) will be based on the same criteria as described for levosimendan above.

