6.2 Efficacy assessments

6.2.1 Slow Vital Capacity

The primary efficacy variable will be the change from baseline at 12 weeks in SVC measured in the supine position, SVC (supine). All SVC measurements prior to 12 weeks will be included in the statistical model. SVC is the maximum volume of air that can be exhaled slowly after slow maximum inhalation. The best read from 3 attempts will be chosen. The volume is measured in litres and the SVC variable will be % of predicted (normal) value for age, height and sex. In

DNO 090017ff823c9bac / 1.0 Approved 32 / 58

addition, time to decline in supine from baseline SVC by \geq 20% and time to supine SVC \leq 50% of predicted will be assessed.

SVC (supine) will be assessed once at each visit during the study including the baseline (visit 1), i.e. in the morning before the study treatment administration.

SVC will be assessed in the sitting and supine position at screening visit. Sitting SVC will be one of the inclusion criteria. Supine SVC is assessed at screening and baseline to ensure that the subject is able to perform it successfully when entering the study.

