7.4 Extent of exposure and treatment compliance

The total number of exposed subjects, the total duration of study treatment exposure (continuous, and categorized both separately and cumulatively at the thresholds of ≤ 4 , ≤ 8 , ≤ 12 , ≤ 24 , and ≤ 48 weeks), and dose levels (in milligrams), averaged over the course of the study as well as at each study visit, will be reported as measures of extent of exposure.

Dose changes will be described by reporting the subject counts in the following categories:

- 1) remained at 1 mg for the entire study (“never increased”)
- 2) uptitrated to 2 mg and remained for the rest of the study (“increased and remained”)
- 3) uptitrated to 2 mg and later downtitrated to 1 mg (“increased, then decreased”).

Dose changes will also be reported by acetylation status.

Treatment compliance will be described by reporting the number of dispensed and returned study treatment capsules at each study visit. The number of subjects with treatment interruptions longer than 7 days will be reported with descriptive statistics.

Both extent of exposure and treatment compliance will be tabulated with descriptive statistics.

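### SAP 6.2.14 item 21 tests a treatment interaction on dose change category, a post-randomisation variable set mainly by on-treatment heart rate, so it is not a randomised subgroup comparison

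*SAP*

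**What the plan says.** SAP 6.2.14 gives the purpose of its list: "Subgroups will be analysed for evidence of a differential treatment effect". An interaction term between treatment and each listed variable is added to the model for the primary SVC endpoint, time to respiratory event and the slope of the ALSFRS-R total score. Items 1 to 20 are, by name or nature, baseline or fixed characteristics. Item 21 is "Dose change category (see section 7.4"), with no separate caveat.

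SAP 7.4 defines three categories by the dosing that followed randomisation: "remained at 1 mg for the entire study"; "uptitrated to 2 mg and remained for the rest of the study"; and increased, then decreased.

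Protocol 5.3.2 makes the dose depend on tolerability, judged mainly by heart rate. At Week 2, if heart rate has "increased > 15 bpm from mean baseline value, the subject will continue with the 1 mg once daily". "At visit 3 (4 weeks) or later visits", a rise above 20 bpm in three recordings returns a subject on 1 mg twice daily to 1 mg once daily. Placebo is titrated in the same way: "Administration of placebo (1 or 2 capsules per day) will be based on the same criteria as described for levosimendan above".

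Protocol 1.1 reports heart rate rises on levosimendan of about 8 bpm versus placebo in heart failure and about 6-8 bpm in stroke/TIA patients. For the phase IIa study in ALS it reports more increased-heart-rate adverse events, in a dose-dependent manner. Protocol 1.2.2 also calls the rise dose-dependent.

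**The concern.** A subgroup interaction can be read as a differential treatment effect when treatment cannot change who is in the subgroup. Here it can. A placebo subject kept at one capsule will typically have had a rise above 15 bpm without drug; a levosimendan subject in the same category may have had it because of the drug. Some in either group may be there for other tolerability reasons or because they stopped early. Titrating placebo makes the interaction estimable but does not make the two groups within a category comparable.

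Timing is a second problem. The category is known only once dosing is over, whereas SVC is judged at Week 12 and a respiratory event may come at any time. Part of the classification can therefore follow the outcome it is meant to explain.

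What is at stake is interpretation. A difference between dose categories looks like a dose-response or tolerability finding, and a reader would naturally take it as one.

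**Working it through.** **Timing, from the documents alone.** Before treatment ends at Week 48, heart-rate-driven reductions can be made at the scheduled visits of Weeks 4, 8, 12, 24 and 36. Protocol 5.3.2 has heart rate assessed before study drug intake, and Protocol 6.2.1 has SVC taken "in the morning before the study treatment administration". A reduction decided at Week 12 or later therefore cannot have influenced the Week 12 SVC. Three of the five visits (Weeks 12, 24 and 36) sort subjects on decisions made at or after that reading. For time to respiratory event, the first event may precede the visit that fixes the category. Death or invasive ventilation, which ends treatment under Protocol 4.5, rules out any later reduction. SAP 7.4 does not say where subjects who stop treatment early are placed.

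**Size, illustration only.** The plan gives no figure for this point, so there is none to reproduce.

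- From the documents: Week 2 limit 15 bpm; heart rate shift 6 or 8 bpm (Protocol 1.1, not ALS patients); SVC SD 10 (SAP 5); 300 levosimendan and 150 placebo subjects.
- Assumed: SD of heart rate change 8, 10 or 12 bpm; correlation ρ between drug-free heart rate change and SVC change; no true SVC effect; the Week 2 rule only, so two categories (kept at 1 mg, increased).

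Formulas, with φ and Φ the standard normal density and distribution function:

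- Share kept at 1 mg = 1 - Φ(a), with a = (15 - shift)/SD on levosimendan and 15/SD on placebo.
- Mean standardised drug-free change among those kept: λ(a) = φ(a)/(1 - Φ(a)).
- False SVC difference among those kept = ρ × 10 × [λ(levosimendan) - λ(placebo)].
- Standard error (SE) in that cell = 10 × √(1/n_L + 1/n_P). The interaction SE sums 1/n over all four cells.
- Rejection rate = Φ(z - 1.96) + Φ(-z - 1.96), where z = interaction bias / interaction SE.

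Worked case, shift 8 and SD 8. Shares are 0.1908 and 0.0304, giving 57.2 of 300 and 4.56 of 150. The λ values are 1.426 and 2.263. At ρ = -0.3 the false difference is -3 × (1.426 - 2.263) = 2.51 points. The cell SE is 10 × √(1/57.2 + 1/4.56) = 4.87, so the ratio is 2.51/4.87 = 0.52.

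All cases at ρ = -0.3:

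| Shift | HR SD | Kept, levosimendan | Kept, placebo | False difference | Cell SE | Ratio | Interaction SE | Rejection |
|---|---|---|---|---|---|---|---|---|
| 6 | 8 | 13.0% (39) | 3.0% (4.6) | 1.91 | 4.95 | 0.39 | 5.06 | 5.9% |
| 6 | 10 | 18.4% (55) | 6.7% (10.0) | 1.48 | 3.43 | 0.43 | 3.59 | 5.7% |
| 6 | 12 | 22.7% (68) | 10.6% (15.8) | 1.20 | 2.79 | 0.43 | 2.99 | 5.5% |
| 8 | 8 | 19.1% (57) | 3.0% (4.6) | 2.51 | 4.87 | 0.52 | 4.98 | 6.4% |
| 8 | 10 | 24.2% (73) | 6.7% (10.0) | 1.94 | 3.37 | 0.58 | 3.54 | 6.2% |
| 8 | 12 | 28.0% (84) | 10.6% (15.8) | 1.58 | 2.74 | 0.58 | 2.95 | 5.8% |

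Among those increased, the false difference at ρ = -0.3 is 0.5-0.8 points, so the interaction bias is 0.6-1.7 points. For those kept at 1 mg, it is 0.8-1.7 at ρ = -0.2, zero at ρ = 0, and -1.2 to -2.5 at ρ = +0.3.

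**Cross-check by simulation.** With a true effect of 3.6 points in everyone, shift 8, SD 10 and ρ = -0.3, the estimates are 5.57 (kept) and 4.43 (increased). The excesses are 5.57 - 3.6 = 1.97 and 4.43 - 3.6 = 0.83, in line with the closed form. Both categories overstate an effect that is the same for all subjects.

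**The case against.** The strongest reply is that SAP 7.5.2 already labels everything outside the hierarchy as supportive, and that this is one of 21 subgroup variables whose test keeps close to its nominal level. That limits the harm, and it stands. A general supportive label does not, however, tell the reader that this one comparison is non-randomised while the others are not.

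The size is also open to challenge. The heart rate SD and the correlation are assumed, and the heart rate shift comes from other patient groups. Measured against the planned 3.6-point difference, the false difference looks large (1.20/3.6 = 33% to 2.51/3.6 = 70%), but that sets a small cell against a whole-trial effect. Against the cell's own standard error it would rarely be visible. This stands: the documents establish non-comparability, not a material distortion.

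A reader might infer that every placebo subject kept at one capsule had a rise above 15 bpm. The documents do not support that. Protocol 1.2.2 treats heart rate as an example of a tolerability reason and also names headache, the study design figure speaks only of good tolerability, and early discontinuers are not placed. Likewise, three of five counts visits, not subjects. Protocol 1.1 puts steady state of the active metabolite at 12-14 days, so many reductions may come early.

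Finally, the test's error rate is barely affected, so a label alone might seem enough. The label is indeed what prevents misreading. But a test declared to look for a differential treatment effect cannot answer that question on this variable, and little is lost by dropping it.

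**Conclusion.** The point holds for item 21 only. Dose change category is affected by treatment and partly determined after the outcomes it would stratify, so its interaction with treatment cannot be read as a differential treatment effect. That conclusion rests on SAP 6.2.14 and 7.4 and Protocol 1.1, 1.2.2 and 5.3.2, and needs no assumed correlation.

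The size does need assumptions. At heart rate SD 8-12 bpm and correlation -0.3, the false SVC difference among subjects kept at 1 mg is 1.2-2.5 points, or 0.4-0.6 of a cell SE of 2.7-5.0. It vanishes at correlation 0, and its direction is unknown, so a reader could not correct for it.

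A reader might infer that the trial's main claim or its type I error control is at risk. It is not: the analysis lies outside the primary test and the hierarchy, and the interaction's own rejection rate is 5.5-6.4% in the illustration. The harm is misinterpretation of a supportive result. The change is worth making because it is cheap.

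**What to change.** Remove item 21 from the treatment-by-subgroup interaction list in SAP 6.2.14 and add:

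> *Outcomes by dose change category will be summarised descriptively by treatment group and labelled as non-randomised comparisons based on a post-randomisation variable; no treatment-by-category interaction will be tested.*

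The label matters as much as the removal, because the descriptive tables show the same non-comparable groups. Acetylation status (item 12) stays in the list as a genetically fixed subgroup related to exposure. No dosing rule changes.

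Cost: one line of SAP text, a few descriptive tables using categories already derived under SAP 7.4, and the loss of three exploratory interaction tests, one per endpoint. No new data are needed.
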